Grade 1: Creatinine >ULN to ≤1.5x ULN	 Monitor creatinine weekly Rule-out other causes (e.g. fluids, medications, i.v. contrast) Promote hydration and cessation of nephrotoxic drugs 	Continue spartalizumab/LAG525 treatment
Grade 2: Creatinine >1.5 - 3.0 x baseline; >1.5 to ≤ 3.0 x ULN	 Monitor creatinine every 2 to 3 days and consult with nephrologist Rule-out other causes (e.g. fluids, medications, i.v.contrast) 	Interrupt spartalizumab/LAG525 until serum creatinine recovers to ≤ Grade 1 or baseline

Nephritis (NCI-CTCAE v5.0)		
Grade	Recommended Adverse Event management guidelines	Mandatory Dose Modification requirements
	 Initiate 0.5 to 1 mg/kg/day prednisone or equivalents if other causes are ruled out If worsening or no improvement: 1 to 2 mg/kg/day prednisone equivalents Promote hydration and cessation of nephrotoxic drugs Consider renal biopsy 	
Grade 3: Creatinine >3.0 x baseline; >3.0 to <6 x ULN	 Monitor creatinine every 1 to 2 days and consider hospitalization Consult with nephrologist and consider renal biopsy Start 1 to 2 mg/kg/day prednisone equivalents Once event improves to Grade ≤1, slowly taper steroids over at least 4-6 weeks 	Permanently discontinue spartalizumab/LAG525
Grade 4: Creatinine > 6.0 x ULN	 Same as Grade 3 hospital for close monitoring and management as per institutional guidelines 	Permanently discontinue spartalizumab/LAG525

^{*}In participants with impaired renal function, dosage of carboplatin should be reduced as per local labeling for carboplatin and hematologic nadirs and renal function monitored.

Table 6-7 Criteria for dose interruption and re-initiation of LAG525 and spartalizumab treatment for potential immune-related pneumonitis

Pneumonitis (NCI-CTCAE v5.0)		
Grade	Recommended Adverse Event management guidelines	Mandatory Dose Modification requirements
Grade 1: Asymptomatic; clinical or diagnostic observations only; intervention not indicated	 Chest imaging/CT scan; repeat imaging in 3-4 weeks or as clinically indicated Monitor symptoms every 2-3 days, clinical evaluation and laboratory work-up for infection; pulse oximetry Consultation with pulmonologist recommended 	Consider interruption of spartalizumab/LAG525

Pneumonitis (NCI-CTC Grade	Recommended Adverse Event management guidelines	Mandatory Dose Modification requirements

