Grade	Recommended Adverse Event management guidelines	Mandatory Dose Modification requirements		
Grade 1 Mild reaction; infusion interruption not indicated; intervention not indicated	 Increase monitoring of vital signs/pulse oximetry as medically indicated until the participant is deemed medically stable in the opinion of the investigator Consider slowing infusion rate until recovery of symptoms 	Continue spartalizumab/LAG525		
Grade 2 Requires infusion interruption but responds promptly to symptomatic treatment (e.g., antihistamines, NSAIDS, narcotics, i.v. fluids); prophylactic medications indicated for < =24 hrs	Stop Infusion and keep line open Additional medical therapy as per local institutional guidelines that may include:	Permanently discontinue spartalizumab/LAG525 in case of recurring infusion reaction despite adequate premedication and prolonged infusion/slow infusion rate		

Infusion reaction (NCI-CTC	AE v5.0)	
Grade	Recommended Adverse Event management guidelines	Mandatory Dose Modification requirements
	participant is deemed medically stable. If symptoms resolve, the infusion may be restarted at 50% of the original infusion rate Premedicate participants approximately 1.5 hrs prior to next infusion of spartalizumab/LAG525 with: Diphenhydramine (50 mg po or equivalent) Acetaminophen (500-1000 mg po or equivalent) Or as per local institutional guidelines	
Grade 3: Prolonged (i.e., not rapidly responsive to symptomatic medication and/or brief interruption of infusion); recurrence of symptoms following initial improvement; hospitalization indicated for other clinical sequelae (e.g., renal impairment, pulmonary infiltrates) Grade 4: Life-threatening; pressor or ventilatory support indicated	Stop Infusion Additional medical therapy as per local institutional guidelines that may include: i.v. fluids Antihistamines NSAIDS Acetaminophen Narcotics Oxygen Corticosteroids Epinephrine Close monitoring of vital signs, pulse oximetry and ECG as medically indicated until the participant is deemed medically stable. Hospitalization as indicated	Permanently discontinue spartalizumab/LAG525

Table 6-10 Criteria for dose interruption and re-initiation of LAG525 and spartalizumab treatment for "other" potential immune-related AEs of special interest

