Other immune mediated events- including but not limited to Autoimmune neuropathy, Demyelinating polyneuropathy, Guillain-Barre syndrome, Myasthenia gravis- like syndrome, Non-infectious myocarditis, pericarditis, pancreatitis, and Grade 3 Fatigue with rapid onset in absence of disease progression, encephalitis, vasculitis, myositis, hemolytic anemia, uveitis

uveitis		T
Grade	Recommended Adverse Event management guidelines	Mandatory Dose Modification requirements
Mild (Grade 1)	Provide symptomatic treatment evaluate/monitor adequately	Continue spartalizumab/LAG525
Moderate (Grade 2)	 Ensure adequate evaluation to confirm etiology or exclude other causes Provide symptomatic treatment Systemic corticosteroids may be indicated Consider biopsy for confirmation of diagnosis. A specialist should be consulted 	Consider interruption of spartalizumab/LAG525 until recovery to ≤ Grade 1 or baseline
Severe (Grade 3)	 Initiate systemic corticosteroids (prednisone or equivalent) at a dose of 1-2 mg/kg/d or equivalent) and other therapies as appropriate Monitor closely and consult with a specialist 	 Interrupt spartalizumab/LAG525 until recovery to ≤ Grade 1 or baseline May restart spartalizumab/LAG525 treatment at the same dose and schedule
		 2nd occurrence: Permanently discontinue spartalizumab/LAG525
Grade 4	Hospitalization and consult with specialist	Permanently discontinue spartalizumab/LAG525
Guillain-Barre Severe peripheral or autonomic neuropathy, or transverse myelitis	Hospitalization and consult with specialist	Permanently discontinue spartalizumab/LAG525
Encephalitis or aseptic meningitis	 Rule out infectious or other causes of moderate to severe neurologic deterioration, and consult with specialist If other etiologies are ruled out, administer corticosteroids at a dose of 1 to 2 mg/kg/day prednisone equivalents 	Permanently discontinue spartalizumab/LAG525
Myasthenia gravis	Consult with specialist	Grade 2

Other immune mediated events- including but not limited to Autoimmune neuropathy, Demyelinating polyneuropathy, Guillain-Barre syndrome, Myasthenia gravis- like syndrome, Non-infectious myocarditis, pericarditis, pancreatitis, and Grade 3 Fatigue with rapid onset in absence of disease progression, encephalitis, vasculitis, myositis, hemolytic anemia, uveitis

Recommended Adverse Event management guidelines Consider pyridostigmine and systemic corticosteroids	Mandatory Dose Modification requirements • Interrupt PDR001 until
	 Interrupt PDR001 until

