 (prednisone or equivalent) at a dose of 1-2 mg/kg/d; other therapies as appropriate (e.g. i.v. lg) Hospitalization in case of severe cases 	recovery to ≤ Grade 1 or baseline Grade ≥3 • Permanently discontinue spartalizumab/LAG525
Urgent cardiology consult is essential to initiate high dose systemic corticosteroids (prednisone or equivalent) (Mahmood et al 2018, Brahmer et al 2018)	Permanently discontinue spartalizumab/LAG525
 Evaluate for pancreatitis (clinical assessment, abdominal imaging and/or MRCP as appropriate) PDR001 may be continued in case of asymptomatic, isolated enzyme elevations without evidence for pancreatitis Initiate steroids in case of ≥ grade 2 acute pancreatitis 	Grade 2 acute pancreatitis: Interrupt PDR001 until recovery to ≤ Grade 1 or baseline Grade ≥3 acute pancreatitis: Permanently discontinue spartalizumab/LAG525
Consult with specialist Consider systemic corticosteroids and other therapies as appropriate (e.g. transfusion) per local institutional guidelines	Permanently discontinue spartalizumab/LAG525
Consult with ophthalmologist	Grade 2 Interrupt PDR001 until recovery to ≤ Grade 1 or baseline Grade 3 and 4 Permanently discontinue
	a dose of 1-2 mg/kg/d; other therapies as appropriate (e.g. i.v. lg) • Hospitalization in case of severe cases Urgent cardiology consult is essential to initiate high dose systemic corticosteroids (prednisone or equivalent) (Mahmood et al 2018, Brahmer et al 2018) • Evaluate for pancreatitis (clinical assessment, abdominal imaging and/or MRCP as appropriate) • PDR001 may be continued in case of asymptomatic, isolated enzyme elevations without evidence for pancreatitis • Initiate steroids in case of ≥ grade 2 acute pancreatitis • Consult with specialist Consider systemic corticosteroids and other therapies as appropriate (e.g. transfusion) per local institutional guidelines

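### Table 6-10: three mandatory Grade 2 holds name only spartalizumab (PDR001), so as written they set no LAG525 hold at Grade 2 onset in Arm 3

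*Protocol*

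**What the plan says.** The title of the table covers both antibodies: "Table 6-10 Criteria for dose interruption and re-initiation of LAG525 and spartalizumab treatment for" other immune-related events of special interest. Three event-specific rows then give a mandatory Grade 2 instruction that names PDR001 alone:

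- **Myasthenia gravis.** The Grade 2 cell begins "Mandatory Dose Modification requirements • Interrupt PDR001 until" and continues "recovery to ≤ Grade 1 or baseline Grade ≥3 • Permanently discontinue spartalizumab/LAG525".
- **Acute pancreatitis.** "Grade 2 acute pancreatitis: Interrupt PDR001 until recovery to ≤ Grade 1 or baseline Grade ≥3 acute pancreatitis: Permanently discontinue spartalizumab/LAG525".
- **Ophthalmology row.** "Grade 2 Interrupt PDR001 until recovery to ≤ Grade 1 or baseline Grade 3 and 4 Permanently discontinue". The row label and the end of the Grade 3/4 line are missing from the text available to us. The row is read as uveitis because it calls for an ophthalmologist and the table heading lists uveitis.

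The management column of the pancreatitis row uses the same drug name in its line on laboratory findings, "PDR001 may be continued in case of asymptomatic, isolated enzyme elevations without evidence for pancreatitis", and also advises "Initiate steroids in case of ≥ grade 2 acute pancreatitis".

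Section 6.5.1.2.1 makes the dose-modification column binding and the management column advisory. Section 6.5.1.1 permits no departure from mandatory interruptions.

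**The concern.** PDR001 is the code for spartalizumab (Section 1.1.3.2). Arm 3 is LAG525 + carboplatin (Section 3), and Section 4.1.1 confirms that it contains no PD-1 inhibitor. A Grade 2 instruction to stop PDR001 therefore has nothing to act on in Arm 3. Read literally, a site with an Arm 3 participant who develops one of these events at Grade 2 is not required to hold LAG525, the only antibody being given.

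This is a participant-safety point, because the event-specific rows exist to be stricter than the general Grade 2 row of the same table. In Arm 3 they lose that effect, and the hold is left to the investigator's judgement.

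**Working it through.** No statistical quantity is involved. The check is a count of the instructions, followed by a search of Section 6.5 for any other rule that would supply the missing hold.

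**1. Count of interruption instructions in the mandatory column.** Lines that only ask the site to consider a hold are not counted.

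| Table | Names spartalizumab/LAG525 | Names PDR001 only |
|---|---|---|
| 6-3 Diarrhea/colitis | 2 (Grades 2, 3) | 0 |
| 6-4 Liver | 1 (Grade 2) | 0 |
| 6-5 Skin | 2 (Grade 2 severe forms, Grade 3) | 0 |
| 6-6 Nephritis | 1 (Grade 2) | 0 |
| 6-7 Pneumonitis | 1 (Grade 2) | 0 |
| 6-8 Endocrine | 2 (symptomatic endocrinopathy, diabetes) | 0 |
| 6-9 Infusion reactions | 0 | 0 |
| 6-10 Other | 1 (Grade 3) | 3 (Grade 2) |
| Total | 10 | 3 |

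10 + 3 = 13, and 3/13 = 0.231. A typical cell from the majority is Table 6-6, Grade 2: "Interrupt spartalizumab/LAG525 until serum creatinine recovers to ≤ Grade 1 or baseline".

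**2. Within-row comparison.** In the myasthenia gravis and pancreatitis rows, the Grade 3-or-higher line of the same cell names both antibodies. The drug name changes between two adjacent lines, and no reason is given for exempting LAG525 at Grade 2.

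**3. Other rules that might require a LAG525 hold at Grade 2 onset in Arm 3.**

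- *General Grade 2 row of Table 6-10.* It names both antibodies but only asks the investigator to consider a hold.
- *Default interruption rule, Section 6.5.1.1.* It covers events that do not appear in the tables. These three do appear.
- *Delay of all drugs for up to 2 weeks, Section 6.5.1.1.* It starts once an event requires an interruption. In Arm 3 these cells require none for LAG525 or carboplatin.
- *Steroid rule, Section 6.5.1.2.2.* It holds both antibodies if prednisone cannot be brought below 10 mg/day before the next dose. The trigger is steroid dose, not grade.
- *Permanent discontinuation list, Section 6.5.1.2.1.* Item 2 (steroids not reduced to 10 mg or less within 12 weeks) and item 3 (Grade 2 or 3 reactions not recovered within 12 weeks) are late backstops.

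None of these is a mandatory LAG525 hold at Grade 2 onset.

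**4. Who is exposed.** The amendment 4 summary gives 88 randomized, 34 of them to Arm 3 (34/88 = 38.6%), and 85 off treatment. That leaves 88 − 85 = 3 on treatment, all in Arm 2, so none in Arm 3. The 38.6% describes past assignment, not people now at risk. The documents give no rates for Grade 2 myasthenia gravis, pancreatitis or uveitis in this trial.

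**The case against.** The best reply is that the practical gap is narrow.

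- **Steroids.** The pancreatitis row advises steroids from Grade 2, and the myasthenia gravis row asks the site to consider them at 1-2 mg/kg/day. Section 6.5.1.2.2 suggests tapering over at least 4 weeks, and cycles are 21 days. A site following that advice would often have to hold the next LAG525 dose anyway. This stands for those two rows, but steroid use is only recommended, so it narrows the gap without closing it. The clearest uncovered case is a Grade 2 event managed without systemic steroids, such as uveitis, and that row label is itself inferred.
- **Nothing forbids a hold.** The ban on departing from mandatory interruptions stops a site from skipping a hold, not from adding one. The title covers both drugs, Section 6.5.1 says to assume that all drugs contribute when causality is unclear, and Section 9.1.1 requires treatment to stop if continuing would harm the participant. This is correct, and many investigators would hold LAG525. It still leaves to judgement what the column is meant to mandate.
- **Arm 2 (and, historically, Arm 1).** There, interrupting spartalizumab can trigger the 2-week delay of all drugs. Whether LAG525 may then resume while spartalizumab stays on hold is unclear: the resumption sentence in Section 6.5.1.1 treats the antibodies as one unit, but other wording there separates them. The point does not rest on those arms.
- **Enzyme-elevation line.** It sits in the advisory column and creates no missing mandatory hold. Changing it is for consistency only.

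**Conclusion.** The concern holds as a minor error. Three of the 13 mandatory interruption instructions name the wrong scope of drug, and in Arm 3 they set no LAG525 hold at Grade 2 onset. The pattern points to a slip and not a deliberate exemption. Amendment 2 records that these tables were aligned with the sponsor's PDR001 standard language, which is a plausible source, but that origin is an inference.

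The conclusion rests on a literal reading of the cells and, for the third row, on taking the ophthalmology row to be uveitis. The PDR001-only wording of that row is legible whatever its label. The current consequence is small, because no Arm 3 participant was on treatment at amendment 4. The response-rate analysis, the decision rule and the sample size do not change.

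**What to change.** In Protocol Table 6-10, replace PDR001 with spartalizumab/LAG525 in the Grade 2 mandatory cells for myasthenia gravis, acute pancreatitis and the ophthalmology (uveitis) row. Make the same replacement in the pancreatitis row's management line on isolated enzyme elevations.

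The cost is four wording replacements. No new data, visits or analyses are needed, and the SAP does not change.

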6.5.1.2.2 Guidance for corticosteroids tapering for management of immune-related AEs

Consultation with disease-specific experts is recommended. Steroids must be tapered slowly and based on response/recovery of clinical symptoms.

Consider complete tapering over a period of at least 4 weeks (sometime 6-8 weeks or longer) to prevent recurrent irAEs. Slower tapering or re-escalation of corticosteroids therapy may be needed if the adverse event is not showing improvement. Once corticosteroid tapering is achieved at a level of 10 mg of prednisone/day (or equivalent) or less, spartalizumab/LAG525 can be restarted as indicated in the dose modification tables. If the dose of prednisone or equivalent cannot be reduced to less than 10 mg/day before the administration of next dose of study treatment, then LAG 525/spartalizumab must be held (note: next dose can be delayed up to 12 weeks).

6.5.1.3 Dose modifications for carboplatin

The local prescribing information should be used for carboplatin dose modifications for the management of myelotoxicity and in participants with impaired kidney function.

6.5.2 Follow-up for toxicities

6.5.2.1 Follow up on potential drug-induced liver injury (DILI) cases

Participants with transaminase increase combined with total bilirubin (TBL) increase may be indicative of potential DILI, and should be considered as clinically important events.

The threshold for potential DILI may depend on the participant's baseline AST/ALT and TBL value; participants meeting any of the following criteria will require further follow-up as outlined below:

- For participants with normal ALT and AST and TBL value at baseline: AST or ALT > 3.0
 x ULN combined with TBL > 2.0 x ULN
- For participants with elevated AST or ALT or TBL value at baseline: [AST or ALT > 2 x baseline AND > 3.0 x ULN] OR [AST or ALT > 8.0 x ULN], combined with [TBL > 2 x baseline AND > 2.0 x ULN]

Medical review needs to ensure that liver test elevations are not caused by cholestasis, defined as ALP elevation > 2.0 x ULN with R value < 2 in participants without bone metastasis, or elevation of ALP liver fraction in participants with bone metastasis.

Note: (The R value is calculated by dividing the ALT by the ALP, using multiples of the ULN for both values. It denotes whether the relative pattern of ALT and/or ALP elevation is due to cholestatic ($R \le 2$), hepatocellular ($R \ge 5$), or mixed ($R \ge 2$ and $R \ge 1$) liver injury.

In the absence of cholestasis, these participants should be immediately discontinued from study treatment, and repeat LFT testing as soon as possible, preferably within 48 hours from the awareness of the abnormal results. The evaluation should include laboratory tests, detailed history, physical assessment and the possibility of liver metastasis or new liver lesions, obstructions/compressions, etc.

- 1. Laboratory tests should include ALT, AST, albumin, creatine kinase, total bilirubin, direct and indirect bilirubin, GGT, prothrombin time (PT)/INR, and alkaline phosphatase.
- 2. A detailed history, including relevant information, such as review of ethanol, concomitant medications, herbal remedies, supplement consumption, and history of any pre-existing liver conditions or risk factors, should be collected.

- 3. Further testing for acute hepatitis A, B, C or E infection and liver imaging (e.g. biliary tract) may be warranted.
- 4. Obtain PK sample, as close as possible to last dose of, if PK analysis is performed in the study.
- 5. Additional testing for other hepatotropic viral infection (CMV, EBV or HSV), autoimmune hepatitis or liver biopsy may be considered as clinically indicated or after consultation with specialist/hepatologist.

All cases confirmed on repeat testing meeting the laboratory criteria defined above, with no other alternative cause for LFT abnormalities identified should be considered as "medically significant", and thus, meet the definition of SAE and should be reported as SAE using the term "potential drug-induced liver injury". All events should be followed up with the outcome clearly documented.

6.6 Additional treatment guidance

6.6.1 Treatment compliance

Study treatment will be dispensed at the site/clinic under the supervision of the investigator and/or study personnel. Records of study medication used, dosages administered, intervals between visits and the completion of the study will be captured in the Drug Accountability Form as well as in IRT. Pharmacokinetic parameters (measures of treatment exposure) will be determined in all participants as detailed in pharmacokinetics section.

6.6.2 Emergency breaking of assigned treatment code

Not applicable.

6.7 Preparation and dispensation

Each study site will be supplied with study drug in packaging as described under investigational and control drugs section. Only qualified and trained personnel to the preparation procedure will handle, prepare and dispense the study drug as described in Pharmacy Manual.

A unique medication number is printed on the study medication label.

Investigator staff will identify the study medication kits to dispense to the participant by contacting the IRT and obtaining the medication number(s). The study medication has a 2-part label (base plus tear-off label), immediately before dispensing the medication kit to the participant, site personnel will detach the outer part of the label from the packaging and affix it to the source document.

6.7.1 Handling of study treatment and additional treatment

6.7.1.1 Handling of study treatment

Study treatment must be received by a designated person at the study site, handled and stored safely and properly and kept in a secured location to which only the investigator and designated site personnel have access. Upon receipt, all study treatment must be stored according to the

instructions specified on the labels and in the [Investigator's Brochure]. Clinical supplies are to be dispensed only in accordance with the protocol. Technical complaints are to be reported to the respective Novartis/sponsor CO Quality Assurance.

Medication labels will be in the local language and comply with the legal requirements of each country. They will include storage conditions for the study treatment but no information about the participant except for the medication number.

The investigator must maintain an accurate record of the shipment and dispensing of study treatment in a drug accountability log. Monitoring of drug accountability will be performed by monitors during site visits or remotely and at the completion of the trial.

At the conclusion of the study, and as appropriate during the course of the study, the investigator will return all unused study treatment, packaging, drug labels, and a copy of the completed drug accountability log to the Novartis/sponsor monitor or to the Novartis/sponsor address provided in the investigator folder at each site.

6.7.1.2 Handling of additional treatment

Not applicable.

6.7.2 Instruction for prescribing and taking study treatment

Dosing and treatment schedule will be performed according to Section 6.1.

All kits of study treatment assigned by the IRT will be recorded in the IRT system.

Additional dosing guidelines for fasting glucose sampling:

On Day 1 of Cycles 1 and 3, a pre-dose fasting (overnight) glucose sample will be collected. The participant must be fasting overnight for at least 10 hours prior to the blood collection for fasting glucose but can freely drink water. A pre-dose pharmacokinetic sample will also be drawn at the same time. After these blood samples, the participant should have a light breakfast prior being administered the study treatment infusions.

Additional dosing guidelines for pharmacokinetic sampling:

On days with pharmacokinetic sampling (Cycle 1 Day 1, Day 8 and Day 15, Cycle 2 Day 1 and Day 8, Cycle 3 Day 1, Day 8 and Day 15, Day 1 of Cycles 4 to 7, End of Treatment visit), the participant does not have to fast overnight unless they are also having a fasting plasma glucose sample taken. The pre-dose sample should be drawn just before study treatment dosing. The sampling time of the pre-dose PK sample and the dosing time of study treatment infusions must be precisely recorded in the eCRF.

7 Informed consent procedures

Eligible participants may only be included in the study after providing (witnessed, where required by law or regulation), IRB/IEC-approved informed consent.

If applicable, in cases where the participant's representative(s) gives consent (if allowed according to local requirements), the participant must be informed about the study to the extent possible given his/her understanding. If the participant is capable of doing so, he/she must indicate agreement by personally signing and dating the written informed consent document.

Informed consent must be obtained before conducting any study-specific procedures (e.g. all of the procedures described in the protocol). The process of obtaining informed consent must be documented in the participant source documents.

Novartis will provide to investigators in a separate document a proposed informed consent form that complies with the ICH GCP guidelines and regulatory requirements and is considered appropriate for this study. Any changes to the proposed consent form suggested by the investigator must be agreed by Novartis before submission to the IRB/IEC.

Information about common side effects already known about the investigational drug can be found in the Investigator's Brochure (IB). This information will be included in the participant informed consent and should be discussed with the participant during the study as needed. Any new information regarding the safety profile of the investigational drug that is identified between IB updates will be communicated as appropriate, for example, via an investigator notification or an aggregate safety finding. New information might require an update to the informed consent and then must be discussed with the participant.

The following informed consent forms are included in this study:

- Main study consent, which also includes:
 - A subsection that requires a separate signature for the 'Optional Consent for Additional Research' to allow future research on data/samples collected during this study
- Pregnancy Outcomes Reporting Consents for female subjects or the female partners of any male subjects who took study treatment
- Patient participation beyond disease progression

Women of child bearing potential must be informed that taking the study treatment may involve unknown risks to the fetus if pregnancy were to occur during the study and agree that in order to participate in the study they must adhere to the contraception requirements.

Male participants must be informed that if a female partner becomes pregnant while he is enrolled in the study, contact with the female partner will be attempted to request her consent to collect pregnancy outcome information.

Participants who will continue study treatment beyond initial disease progression as per RECIST 1.1 criteria have to be re-consented. These participants must sign a new, witnessed IRB/IEC-approved informed consent form which will detail alternative available therapies.

As per section 4.6, during a Public Health emergency as declared by Local or Regional authorities (i.e. pandemic, epidemic or natural disaster), that may challenge the ability to obtain

a standard written informed consent due to limits that prevent an on-site visit, Investigator may conduct the informed consent discussion remotely (e.g. telephone, videoconference), if allowable by a local Heath Authority. Guidance issued by local regulatory bodies on this aspect prevail and must be implemented and appropriately documented (e.g. the presence of an impartial witness, sign/dating separate ICFs by trial participant and person obtaining informed consent, etc.).

A copy of the approved version of all consent forms must be provided to Novartis after IRB/IEC approval.

8 Visit schedule and assessments

The Assessment Schedule (Table 8-1) lists all of the assessments and indicates with an "X", the visits when they are to be performed. All data obtained from these assessments must be supported in the participant's source documentation.

Participants should be seen for all visits/assessments as outlined in Table 8-1 or as close to the designated day/time as possible. Missed or rescheduled visits should not lead to automatic discontinuation. Participants who prematurely discontinue the study for any reason should be scheduled for a visit as soon as possible, at which time all of the assessments listed for the final visit will be performed. At this final visit, all dispensed investigational product should be reconciled, and the adverse event and concomitant medications recorded on the CRF.

1 4510 0-1	A330331																	
Period	Screening	Treat	ment								End of Treatment (EOT)	Follov	v-up³					
Visit Name	Screening	e 1	e 1	e 1	Cycl e 2 Day 1	Cycl e 2 Day 8	Cycl e 3 Day 1	e 3	Cycl e 3 Day 15	Subseq. cycles Day 1	End of Treatment (EOT)	30 day Safet y F- up	60 day Safet y F- up	90 day Safet y F- up	120 day Safet y F- up	150 day Safet y F- up	End Post Treatme nt Follow- up	Surviv al F- up ⁴
Days	-21 to -1	1	8 ±1	15 ±1	22 ±1	29 ±1	43 ±1		57 ±1	- ±3	-	- -0 +7	- ±7	- ±7	- ±7	- -0 +14	-	-
Informed consent	Х																	
IRT registration	Х										Х							
IRT randomization		х																
Treatment beyond progression ICF		for pa	ırticipa	nts wh	o mee	t the c	riteria (outline	d in Se	ection 6.1.5.1								
Demography	Х																	
Inclusion / Exclusion criteria	х																	
Medical history/current medical conditions	х																	
BRCA status if known	х																	
Locally confirmed TNBC status in advanced setting	х																	

Novartis			Co	onfidential		Page 83 of 185
Amended Protoc	ol Version 0	4 (Clean)				Protocol No. CLAG525B2101
Period	Screening	Treatment	т	End of reatment EOT)	Follow-up ³	

Period	Screening	Treat	ment								End of Treatment (EOT)	Follov	v-up³					
Visit Name	Screening	Cycl e 1 Day 1	Cycl e 1 Day 8	e 1		e 2	Cycl e 3 Day 1	Cycl e 3 Day 8	Cycl e 3 Day 15	Subseq. cycles Day 1	End of Treatment (EOT)	30 day Safet y F- up	60 day Safet y F- up	90 day Safet y F- up	120 day Safet y F- up	150 day Safet y F- up	End Post Treatme nt Follow- up	Surviv al F- up ⁴
Days	-21 to -1	1	8 ±1	15 ±1			43 ±1	50 ±1	57 ±1	- ±3	-	- -0 +7	- ±7	- ±7	- ±7	- -0 +14	-	-
Diagnosis and extent of cancer	х																	
Prior/concomitant medications										w-up or start of ne tions relative to the						d.		
Antineoplastic therapies (prior/since discontinuation of study treatment)	х										x	x	x	x	x	x	х	
Physical Examination	s	s			S		s			S	s							
Performance status	Х	х			X		x			x	Х	х						
Body Height	Χ																	
Body Weight	Χ	Χ			Χ		Χ			X	X							
Vital Signs	Χ	Χ	Χ	Х	Χ	Χ	Χ	Χ	Χ	X	X	Χ						
Hematology	Χ	Х	Χ	Χ	Χ	Χ	Χ			X	X	Χ						
Chemistry	Χ	Χ	Χ	Χ	Χ	Χ	Χ			X	X	Χ						
Thyroid Panel- TSH	×				X		X			x	×	Х						
Thyroid Panel- Free T3; Free T4	х	Only i	if TSH	is abn	ormal	_		_				_						

Period	Screening	Treat	ment								End of Treatment (EOT)	Follow	/-up³					
Visit Name	Screening	e 1		e 1	Cycl e 2 Day 1	e 2	Cycl e 3 Day 1		Cycl e 3 Day 15	Subseq. cycles Day 1	End of Treatment (EOT)	30 day Safet y F- up	day Safet	90 day Safet y F- up	120 day Safet y F- up	150 day Safet y F- up	End Post Treatme nt Follow- up	Surviv al F- up ⁴
Days	-21 to -1	1	8 ±1	15 ±1	22 ±1	29 ±1	43 ±1		57 ±1	- ±3	-	- -0 +7	- ±7	- ±7	- ±7	- -0 +14	-	-
Hepatitis testing	Х	If clini	ically in	ndicate	ed perf	orm te	sting a	s need	led									
Local HIV testing, if required per local requirements/reg ulations	S																	
Cytokines for safety	Х	Anytir AE	ne wh	en a sı	uspect	ed cyto	okine r	elease	syndr	ome occurs, imme	diately after t	he AE,	and on	e week	after o	ccurren	ce of the	
Coagulation	Х	Х			Х		Х			Х	Х	Х						
Cardiac Troponin	Х			Χ		Χ	Х		Х									
Urinalysis (macroscopic)	S				s		s			S	S							
Urinalysis (microscopic)	Any time dip	stick u	rinalys	is is al	bnorma	al												
Pregnancy Test (serum) ¹	≤72 hours before first dose of study treatment										х	х				x		
Pregnancy test (urine)					S		S			S			S	S	s			

Period	Screening	Treat	ment								End of Treatment (EOT)	Follov	v-up³					
Visit Name	Screening	e 1	Cycl e 1 Day 15 Day 1 Da											day Safet y F-	End Post Treatme nt Follow- up	Surviv al F- up ⁴		
Days	-21 to -1	1	8 ±1	15 ±1	22 ±1	29 ±1	43 ±1	50 ±1	57 ±1	- ±3	-	- -0 +7	- ±7	- ±7	- ±7	- -0 +14	-	-
Tumor evaluation (CT scan/MRI/Bone scan)	-28 to -1	8-2 for	r imagir	weeks (+/- 1 week) for the first 9 months and every 12 weeks (+/- 1 week) thereafter, aging collection plan and Section 8.3.1. Upon the approval of amendment 4, the tumor assessments during the post-treatment efficacy period will be now optional and will be left at the discretion of the investigator.														
Chest X-ray		If clini	ically i	ndicate	ed													
ECG (Central)	At least 72 hours prior randomizati on	x					х				x							
ECG (Local)		s			s		s			On Day 1 of every 2 cycles after cycle 3								
Cardiac imaging (MRI/ECHO)	Х	If clini	linically indicated X															
Adverse Events			up to Day 150; non-suspected AE up to Day 150 or start of new post treatment anti-neoplastic medication, oner. See Appendix 1 (Safety follow-up diagram)															
Serious Adverse Events			to Day 150 and beyond; non-suspected SAE up to Day 150 or start of new post treatment anti-neoplastic medication, whichever is ndix 1 (Safety follow-up diagram)															

Novartis	Confidential	Page 86 of 185
Amended Protocol Version 04 (Clean)		Protocol No. CLAG525B2101

Period	Screening	Treat	ment								End of Treatment (EOT)	Follow	v-up³					
Visit Name	Screening	Cycl e 1 Day 1	Cycl e 1 Day 8	Cycl e 1 Day 15	Cycl e 2 Day 1	Cycl e 2 Day 8	Cycl e 3 Day 1	Cycl e 3 Day 8	e 3	Subseq. cycles Day 1	End of Treatment (EOT)	30 day Safet y F- up	60 day Safet y F- up	90 day Safet y F- up	120 day Safet y F- up	150 day Safet y F- up	End Post Treatme nt Follow- up	Surviv al F- up ⁴
Days	-21 to -1	1	8 ±1	15 ±1	22 ±1	29 ±1	43 ±1	50 ±1	57 ±1	- ±3	-	- -0 +7	- ±7	- ±7	- ±7	- -0 +14	-	-
Newly obtained tumor sample ²	Х																	
LAG525 infusion		Day 1	of eac	ch cycl	e (21 d	days) ι	ıntil EC	DΤ										

Period	Screening	Treat	ment								End of Treatment (EOT)	Follow	v-up³					
Visit Name	Screening	e 1	Cycl e 1 Day 8		e 2	e 2	e 3	e 3	Cycl e 3 Day 15	Subseq. cycles Day 1	End of Treatment (EOT)	30 day Safet y F- up	60 day Safet y F- up		120 day Safet y F- up	150 day Safet y F- up	End Post Treatme nt Follow- up	Surviv al F- up ⁴
Days	-21 to -1	1	8 ±1	15 ±1	22 ±1	29 ±1	43 ±1	50 ±1	57 ±1	- ±3	-	- -0 +7	- ±7	- ±7	- ±7	- -0 +14	-	-
spartalizumab infusion		Day 1	of ea	ch cyc	e (21 d	days) ເ	until E0	OT	•	,								
carboplatin infusion		Day 1	l of ea	ch cyc	e (21 d	days) ເ	until E0	ЭТ										
PK sampling		of Cy		to 7, E						08, C3D15, Day 1 8 for PK								
Immunogenicity (IG) sampling			ay 1 o		s 1 to	7, EO	Γ - See	Table	8-7 fc	r immunogenicity								
Participant's disposition	Х										X						x	
Efficacy followup ³																	х	
Safety followup visit ³												Х				Х		
Safety follow-up Call ³													s	s	s			
Survival followup ^{3,4}																		

S =Assessment to be recorded in the source documentation only

X = assessment to be recorded in the clinical database or received electronically from a vendor

¹ by Central Laboratory, unless participant is postmenopausal (see Exclusion Criterion 23 for definition of postmenopausal status)

Novartis Confidential Page 88 of 185
Amended Protocol Version 04 (Clean) Protocol No. CLAG525B2101

² If new tumor sample cannot be obtained, archival tumor sample obtained maximum 6 months prior to start of study treatment is acceptable providing the participant has not received antineoplastic therapy since then.

³ For ongoing participants who will transfer into PTA program (roll over study or PSDS) only EOT visit will be performed but no safety, efficacy and survival follow-up.

⁴ Follow-up duration is limited to 150 days after the last dose of LAG525 and/or spartalizumab (whichever was stopped last). If carboplatin was stopped more than 150 days after LAG525 and/or spartalizumab, the participant can be discontinued 30 days after the last dose of carboplatin. Survival follow-up period is removed after Protocol Amendment #4 is approved.

